1.4. Rationale for This Study

Tenofovir DF-associated bone toxicities have not been well understood in children. One theory is that Tenofovir DF may stimulate bone reabsorption which can be detected with increases in bone markers and calcium excretion. Among children and adolescents, skeletal growth increases and these same indicators may be expected to be present in children without Tenofovir DF exposure. Bone events or abnormalities, such as fractures, related to both proximal renal tubulopathy (PRT) and loss of BMD have been documented in both control and

Tenofovir DF-receiving arms in adult HIV trials. Among HIV-1 positive adolescents (GS-US-104-0321), the Tenofovir DF-receiving arm reported osteopenia in 6.7% of subjects (3/45) and 4.8% (2/42) in the placebo group, and among HBV infected adolescents, there were no reported bone events meeting the safety criteria of $\geq 6\%$ BMD loss (GS-US-174-0115). In pediatric clinical trials of HIV-1 infected children (2-11 years), no bone events associated with BMD loss were reported up through 144 weeks of follow up time (GS-US-104-0352).

In a limited study of six pediatric subjects taking Tenofovir DF, two children developed BMD decreases of greater than 6% over the course of treatment. Contrary to these findings was a cross over trial from Italy where no notable decreases in BMD were detected when pediatric patients taking d4T and protease inhibitor HIV treatment regimens switched to Tenofovir DF/3TC/EFV. The Collaborative HIV Paediatric study (CHIPS) based in Ireland and the UK, reported no BMD decreases in their longitudinal cohort {15423}. Among HIV infected adults taking Tenofovir DF, the observed pattern is that BMD loss is sustained early in the therapeutic course [TIME] and stabilizes with no further notable BMD loss; this pattern has not been established in the limited registered studies on either HIV or HBV infected children.

Renal toxicity associated with Tenofovir DF has been previously identified in small subsets of study participants across randomized controlled clinical trials. In an NIH systematic review of Tenofovir DF's renal safety profile, the mean difference in reduction of creatinine clearance among subjects on Tenofovir DF was 3.92 mL/min (2.13-5.70 mL/min 95% confidence interval) compared to controls, and no clear associations between treatment and proteinuria, hypophosphatemia, nor fractures. A modest increase in risk of acute renal injury (0.7%, 0.2-1.2% 95% confidence interval) was noted. The clinical impact of these findings is unknown {16177}. Among registered studies the detection on renal toxicities has been very low, ranging between 1 to 2%. Detailed information and sequelae as a result of serious renal toxicities, such as Fanconi syndrome, come from case series or single reports. A recent NIH report documented 7 of 51 (14%) adult patients treated for CHB with Tenofovir DF (and/or adefovir) who developed renal tubular dysfunction after 22 to 94 months on therapy. Subjects with renal tubular dysfunction had an average age of 58, and 6 of the 7 were male. All affected subjects had hypophosphatemia, with others having one or more indications of hypouricemia, increased serum creatinine, proteinuria, or glycosuria {20768}.

The available data to characterize the incidence of renal toxicities in children is lacking, and collected primarily within registration studies of CHB and Tenofovir DF. As Tenofovir DF also has the indication for treatment of pediatric HIV, the drug's safety profile has some overlay to both the HIV and the HBV-infected populations. Among pediatric subjects completing 144 weeks of treatment in clinical trial GS-US-104-0352, 4 of 89 (4.5%) patients discontinued Tenofovir DF treatment for HIV-1 as a result of new onset adverse reactions suggestive of PRT (e.g., glycosuria, hypophosphatemia).

Data from Collaborative HIV Pediatrics Study (CHIPS) in Ireland and the UK reported that among the 159 HIV-1 positive children taking Tenofovir DF (since 2001) of a cohort of 1253 participants, 6 (3.8%) developed renal toxicities including PRT, Fanconi syndrome, and acute renal failure. Five of the six were also taking concurrent NRTI and PI combinations, and

were receiving a higher concentration of Tenofovir DF (two were greater than 120% of the recommended Tenofovir DF dosing regimen), likely due to advanced disease {13569}. A study derived from the same CHIPS cohort evaluated renal toxicities and of those 456 participants on antiretroviral therapy, 20 developed hypophosphatemia (4.4%), 10 of whom were on Tenofovir DF (2.2%). Incidence of hypophosphatemia associated with Tenofovir DF was 4.3/100 person-years and among controls (not exposed to Tenofovir DF) it was 0.9/100 person-years. Recommendations from these studies include longitudinal monitoring of renal function {15423}.

Independent and sponsored studies in recent years have shown that Tenofovir DF use among adults with diagnoses of HBV or HIV carries a modest risk of BMD decreases or acute renal injury compared to placebo or other non-Tenofovir DF containing treatments. Reported decreases in bone mineral density among patients on Tenofovir DF therapy compared to age- and height adjusted bone density scores are rare across all age strata seen in clinical trials and observational studies (GS-US-104-0321, GS-US-104-0352, GS-US-174-0115). Among HIV- and HBV-infected adolescents and children, understanding the longitudinal risk of changes in bone mineral density is critical for managing Tenofovir DF-treatment plans weighed against any possible alterations to bone development in children.

Adverse event data from Gilead-sponsored trials have shown increases in creatinine among 0.2% of subjects, and renal failure in 0.06%. In the Viread® Expanded Access Program, 0.04% of subjects were diagnosed with new onset PRT (including Fanconi syndrome). In pediatric HIV study GS-US-104-0352, 0.05% of patients between 2 and 12 years of age developed PRT; there were no reports of PRT in the parallel trial among adolescents with HIV. Some mediating factors identified in past studies have included advancing age, pre-existing renal insufficiencies, use of known nephrotoxic medications, and low weight. Renal injuries while on Tenofovir DF treatment have been reversible after discontinuation of Tenofovir DF with complete resolution within 4 months for the majority of subjects. The follow up period and sample size of study subjects reporting renal injury have been limited and it is prudent to evaluate these potential risks over a longer timeframe and under real world conditions.

Among adolescent patients with CHB, available interim 72 Week clinical trial data indicate that 5.8% (95% confidence band of 1.2-15.9%) of subjects experienced a $\geq 4\%$ decrease in BMD; by comparison 3.7% (95% CI 0.4-12.5%) of placebo controls had a BMD loss of $\geq 4\%$. In this same trial, no renal adverse drug reactions were detected by Week 72. Detecting renal or bone AEs in CHB adolescents taking Tenofovir DF are infrequent events, and the pool of Tenofovir DF-naïve subjects within the EU suitable for enrollment is limited. With a fixed sample size of 100 (50 in each monitoring group) one would expect to detect 4-5 renal or bone adverse drug reactions across both real-world groups (both receive equivalent treatment) over 96 weeks.

1.5. Compliance

This study will be conducted in compliance with this protocol, Good Clinical Practice (GCP), and all applicable regulatory requirements.

2. OBJECTIVES

The primary objective of this study is as follows:

- To characterize the long term (i.e., 96 weeks of follow up) bone safety profile of open-label Tenofovir DF treatment in CHB-infected adolescents. This includes prospectively evaluating and comparing the bone mineral density (BMD) change between CHB- infected adolescents 12 to < 18 years of age treated with Tenofovir DF in European treatment centers who are assigned to one of two schedules for renal and bone laboratory monitoring and BMD measurement. Primary study endpoint will be the percent changes in BMD from Baseline through study Week 96.

The secondary objectives of this study are as follows:

- To document all serious adverse drug reactions (SADR) and all renal- and bone-related adverse events (AEs), including renal and bone laboratory abnormalities
- To determine the time to diagnosis of renal and bone AEs and document the resulting patient management and outcome(s)
- To assess the clinical management and outcomes of renal- and bone-related \geq Grade 3 laboratory markers and clinical SAEs.
- To assess the efficacy and tolerability of Tenofovir DF in adolescents with CHB infection
- To assess the use of oral vitamin D, calcium and phosphate supplementation and explore the association between supplement use and rates of bone and renal AEs
- To describe the demographics and disease characteristics of adolescents with CHB infection treated with Tenofovir DF.

3. STUDY DESIGN

3.1. Endpoints

The primary endpoint of this study is:

- The identification of bone AEs occurring in subjects taking Tenofovir DF between Baseline and Week 96 of treatment including the identification of $\geq 4\%$ reduction in BMD within subjects and between monitoring groups from Baseline.

The secondary endpoints of this study are:

- Documentation of renal or bone AEs and outcomes among subjects receiving Tenofovir DF, including time to medication withdrawal or discontinuation
- Subjects' cumulative exposure time on Tenofovir DF at the time renal or bone AEs are detected up to and including Week 96 or to study discontinuation (subjects without renal or bone AEs will contribute cumulative exposure time on Tenofovir DF from Baseline to Week 96 or to study discontinuation). The cumulative time to renal or bone AEs will be expressed as incident rates.
- Documentation of the medical management and classification of detected renal or bone laboratory abnormalities
- Analysis of subjects' virological and immunological status from Baseline to Week 96 under real world treatment practices
- Report provider recommendations and subject adherence to dietary supplements (e.g., Vitamin D, calcium)
- Documentation of subject demographics, new medical issues, medications, biometrics, treatment adherence
- Reasons for discontinuation of Tenofovir DF

3.2. Study Design

The study will be a prospective cohort comprised of HBV infected adolescents who initiate Tenofovir DF therapy in clinics across Europe. The subjects will be assigned to one of two monitoring groups using a validated computer-generated tool for randomization. Subjects will be assigned to Group 1 or 2 upon enrollment into the study but prior to Baseline laboratory and DEXA imaging assessments.

DEXA scans are non-invasive tests to measure bone mineral density as well as skeletal maturity and bone mass. DEXA scans emit an average effective dose of 0.001 milli Sieverts (mSv) in adults {22238}. These scans emit very minor radiation (i.e., in comparison, one mammogram has an effective dose of 0.4 mSv), and with such low doses of radiation do not pose concerning health hazards. Data are based on adult studies and may have a higher relative effective dose, particularly in very young children. Repeated DEXA scans should be conducted using the same model of equipment, if possible, and scans should be read in a standardized manner.

Group 1 will receive Tenofovir DF for the treatment of CHB infection, followed over 96 weeks using an enhanced monitoring protocol which includes more frequent laboratory bone biomarker testing and lumbar spine and whole-body DEXA scans than specified for Group 2. With the exception of an enhanced monitoring protocol for bone and renal outcomes, subjects will be managed according to local standards of care.

Group 2 will be the comparator group of subjects receiving Tenofovir DF for the treatment of CHB infection and with the exception of pre-specified bone monitoring, managed according to local standards of care. Group 2 will receive bone biomarker testing, lumbar spine and whole-body DEXA at Baseline, Weeks 48 and 96.

Both groups will be monitored for 96 weeks on Tenofovir DF during clinic visits for response to treatment, AEs, adherence to supplementary vitamins and mineral intake assessments.

Both groups will be required to have DEXA (whole body and spine) scans for BMD at Baseline (week 0) and prior to receipt of Tenofovir DF, and at the end of the study period (Week 96). Group 2 will be a comparator cohort to Group 1 in evaluating the hypothesis of whether enhanced monitoring for renal and BMD changes and AEs provides a net benefit in preventing renal- or bone-related adverse outcomes to adolescents receiving Tenofovir DF therapy for HBV.

For this study design and limited age groupings, matching at enrollment on other factors such as demographics, would likely have a marginal benefit on the strength of the results; matching may occur (e.g., age, gender, ethnicity, duration of Tenofovir DF exposure) during the analysis phase as specified in the statistical analysis plan (SAP).

The strengths of the study include a focus on long term outcomes related to renal and bone adverse event reporting in a vulnerable population. Use of two real world cohorts will permit the evaluation of whether a schedule of more frequent clinical assessments of adolescent patients on Tenofovir DF benefit from early detection of potential AEs. Previous studies across multiple HIV and HBV infected patient populations have demonstrated a modest risk for both bone and renal AEs related to Tenofovir DF-containing medications. Understanding whether changes in monitoring frequency for serum and urine biomarkers and use of more frequent DEXA may provide early detection to subtle changes in bone or renal dynamics and be beneficial in enhancing patient outcomes.

The feasibility of study design implementation has been assessed using clinical trials data from GS-US-174-0115. Demographic, adverse event reporting, clinical and laboratory markers, and DEXA screen results at baseline and at regular intervals from clinical trials show a range of 90-100% reporting adherence for key variables, when applicable.

The primary safety analysis will be conducted after the last assigned subject reaches Week 96 of Tenofovir DF treatment.

Subjects with the following characteristics will be eligible for enrollment: 12 to <16 years of age with chronic HBeAg-positive or HBeAg-negative HBV infection (e.g., HBsAg-positive for at least 6 months)

Subjects must be naïve to Tenofovir DF, but could have received prior treatment with other anti-HBV nucleoside/nucleotide therapy or interferon (e.g., treatment failure). Previous treatment with interferon should have ended at least six months prior to the Screening Visit.

Screening measures for Monitoring Groups 1 and 2 will include determining a subject's eligibility into the study with the following criteria: current age, documentation of chronic HBV infection, prior Tenofovir DF exposure, weight, laboratory assessments, ability to swallow solid tablets, subject's ability to adhere to treatment regimen, obtaining written informed consent from subject's parent or legal guardian or obtain informed assent from the subject

Baseline measures for Monitoring Groups 1 and 2 will include laboratory assessments for HBV DNA, HBV serology, HCV, HDV, and HIV polymerase chain reaction (PCR) testing, HBV genotyping, serum renal and bone chemistries, liver function, hematology, urinalysis. DEXA imaging, a physical exam (including pregnancy testing for females), current concomitant medications and any reported prior bone and renal AEs, will also be collected.

FREQUENCY OF STUDY PROCEDURES ([Appendix 2](#)):

Subjects enrolled to either Group 1 or 2 will have the following measures assessed:

- HBV DNA: every 12 weeks
- HBV serology: every 24 weeks
- Liver chemistry (i.e., alanine aminotransferase (ALT), alkaline phosphatase (ALP), aspartate aminotransferase (AST), total and direct bilirubin, total protein, albumin, gamma glutamyl transpeptidase (GGT), lactate dehydrogenase (LDH), creatine kinase (CK) every 24 weeks
- Hematology (i.e., complete blood count with differential and platelets, PT/INR): every 24 weeks
- Physical Examination and Drug Dispensing: every 12 weeks
- Documentation of bone or renal AEs since the subject's last visit
- Documentation of medical management in the event of bone or renal AEs

Subjects enrolled to Group 1 will have the following additional monitoring;

- DEXA: every 24 weeks from Baseline to Week 96 (5 scans)
- Serum bone chemistry (i.e., calcium, phosphorus, vitamin D levels (25-hydroxy and 1, 25 dihydroxyvitamin), parathyroid hormone (PTH), osteocalcin, bone-specific alkaline phosphatase, N and C telopeptides): every 24 weeks
- Serum renal chemistry (i.e., glucose, creatinine, calculated creatinine clearance, magnesium, bicarbonate, chloride, potassium, sodium): at 4 weeks and 12 weeks from Baseline and every 12 weeks thereafter, according to SmPC
- Urinalysis (i.e., protein, glucose, creatinine, phosphate, bicarbonate, blood, calcium): at 4 weeks and 12 weeks from Baseline and every 12 weeks thereafter

Subjects enrolled to Group 2 will have the following monitoring:

- DEXA: every 48 weeks from Baseline to Week 96 (3 scans)
- Serum bone chemistry (i.e., calcium, phosphorus, vitamin D levels (25-hydroxy and 1,25 dihydroxyvitamin), PTH, osteocalcin, bone-specific alkaline phosphatase, N and C telopeptides): every 48 weeks
- Serum renal chemistry and urinalysis according to local standards of care

Subjects who permanently discontinue Tenofovir DF will be asked to return for an end of treatment visit within 72 hours of the last dose of Tenofovir DF. Subjects who permanently discontinue Tenofovir DF will be followed for 24 weeks off treatment or up to initiation of local standard of care treatment, whichever occurs first.

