6.4.1. Group 1: Week 4 Assessments

The following evaluations will be performed at Week 4 unless otherwise specified. Study visits are to be completed ± 7 days of the protocol-specified visit date, based on the Baseline Visit. Week 4 assessments are outlined in the following section (Section 6.4.4). Group 2 subjects will follow local standard of care for renal monitoring and AE collection.

The following assessments and procedures will be performed and recorded on CRFs:

- Changes in medical status or symptoms from prior visit

- Body weight and height
- Blood samples for:
 - Serum renal chemistry (creatinine, glucose, creatinine clearance (calculated), magnesium, bicarbonate, chloride, potassium, sodium), fasting required
- Urinalysis (protein, glucose, creatinine, phosphate, bicarbonate, blood, calcium) , fasting required
- Assessment of medication adherence
- Review of bone and renal AEs and any associated medical management
- Tenofovir DF dispensing and instructions on appropriate dosing and administration
- Concomitant medications (including dietary supplements such as calcium, vitamin D, phosphorus)

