6.4.2. Group 1: Week 12 and 36 Assessments

Study Visit for Weeks 12 and 36 should be completed \pm 7 days of the protocol-specified visit date, based on the Baseline Visit. Group 2 subjects will follow local standard of care for renal monitoring and AE collection. The following assessments and procedures will be performed and recorded on CRFs:

- Complete physical examination including, vital signs, body weight and height
- Group 1: Urinalysis (protein, glucose, creatinine, phosphate, bicarbonate, blood, calcium), fasting required
- Blood samples for:
 - Group 1: Serum renal chemistry (creatinine, glucose, creatinine clearance (calculated), magnesium, bicarbonate, chloride, potassium, sodium), fasting required
 - Plasma HBV DNA (PCR method)
- Review of bone and renal AEs and any associated medical management
- Concomitant medications (including dietary supplements such as calcium, vitamin D, phosphorus)
- Assessment of medication adherence
- Tenofovir DF dispensing and instructions on appropriate dosing and administration

- Screening for pregnancy (urine screen)

Subjects who discontinue the study prior to the Week 12 or 36 Visit will complete all Week 12 or 36 assessments and procedures at an Early Drug Discontinuation Visit, to be completed within 72 hours of last dose of Tenofovir DF. Subjects who have received at least one dose of Tenofovir DF and permanently discontinue treatment will be followed for 24 weeks off treatment or up to initiation of an alternative treatment regimen, whichever occurs first.

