6.4.5. Groups 1 and 2: Week 60 and 84 Assessments

Study Visit for Weeks 60 and 84 should be completed \pm 7 days of the protocol-specified visit date, based on the Baseline Visit. Group 2 subjects will follow local standard of care for renal monitoring. The following assessments and procedures will be performed and recorded on CRFs:

- Complete physical exam including vital signs, body weight and height
- Blood samples for:
 - Plasma HBV DNA (for PCR)
 - Group 1: Serum renal chemistry (glucose, creatinine, creatinine clearance (calculated), magnesium, bicarbonate, chloride, potassium, sodium), fasting required
- Group 1: Urinalysis (glucose, protein, creatinine, phosphate, bicarbonate, blood, calcium), fasting required
- Review of bone and renal AEs and any associated medical management
- Concomitant medications (including dietary supplements such as calcium, vitamin D, phosphorus)
- Assessment of medication adherence
- Tenofovir DF dispensing and instructions on appropriate dosing and administration
- Screening for pregnancy (urine screen)

Subjects who discontinue the study prior to the Week 60 or 84 Visit will complete all Week 60 or 84 assessments and procedures at an Early Drug Discontinuation Visit, to be completed within 72 hours of last dose of Tenofovir DF. Subjects who have received at least one dose of

Tenofovir DF and permanently discontinue treatment will be followed for 24 weeks off treatment or up to initiation of active treatment, whichever occurs first.

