7.5.5. Management of Reduced Serum Phosphate

If serum phosphate is confirmed to be $< 3.0 \text{ mg/dl}$ (0.96 mmol/l) in any paediatric patient receiving Tenofovir DF, renal function should be re-evaluated within one week, including measurements of blood glucose, blood potassium and urine glucose concentrations. If renal abnormalities are suspected or detected then consultation with a nephrologist should be obtained to consider interruption of Tenofovir DF treatment.

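### Serum phosphorus is not listed at 5 of the 9 Group 1 post-baseline renal draws, although Protocol 7.5.5 acts on a low serum phosphate; adding it is a cheap improvement (minor to moderate)

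*Protocol*

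**What the plan says.** Protocol 3.2 gives the Group 1 serum renal schedule as "calculated creatinine clearance, magnesium, bicarbonate, chloride, potassium, sodium): at 4 weeks and 12 weeks from Baseline and every 12 weeks thereafter, according to SmPC". The visit sections repeat the same analytes without phosphorus. Week 4 (6.4.1) has "Serum renal chemistry (creatinine, glucose, creatinine clearance (calculated), magnesium, bicarbonate, chloride, potassium, sodium), fasting required", Weeks 12 and 36 (6.4.2) have "Group 1: Serum renal chemistry (creatinine, glucose, creatinine clearance (calculated), magnesium, bicarbonate, chloride, potassium, sodium), fasting required", and Weeks 60 and 84 (6.4.5) have "Group 1: Serum renal chemistry (glucose, creatinine, creatinine clearance (calculated), magnesium, bicarbonate, chloride, potassium, sodium), fasting required". The synopsis, the screening and baseline sections and the Appendix 2 definition agree.

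The serum analyte sits in the other panel: "Serum bone chemistry (i.e., calcium, phosphorus, vitamin D levels" and further bone markers. Group 1 has that panel every 24 weeks and Group 2 every 48 weeks.

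Section 7.5.5 opens with "If serum phosphate is confirmed to be $< 3.0 \text{ mg/dl}$ (0.96 mmol/l) in any paediatric patient receiving Tenofovir DF" and goes on: "renal function should be re-evaluated within one week, including measurements of blood glucose, blood potassium and urine glucose concentrations". It gives no interval at which serum phosphate should be tested.

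Two provisions limit the gap. Group 1 also has "Urinalysis (i.e., protein, glucose, creatinine, phosphate, bicarbonate, blood, calcium): at 4 weeks and 12 weeks from Baseline and every 12 weeks thereafter". The Appendix 2 footnote leaves Group 2 renal monitoring to local standard of care, which may include the SmPC intervals.

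**The concern.** Section 7.5.5 is triggered by a single serum analyte. In the arm meant to have enhanced renal monitoring, that analyte follows the bone calendar, while the tests in the 7.5.5 work-up follow the denser renal calendar. A low serum phosphate arising in the first months would have no scheduled test to show it before Week 24. The early discontinuation visit has the same gap for subjects who stop before Week 12, 36, 60 or 84, because they complete the list for that visit.

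At stake are subject safety and the secondary renal aims: time to diagnosis (Protocol 2) and whether more frequent assessment gives earlier detection (Protocol 3.2). The BMD primary objective is not affected.

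The protocol's own evidence on the value of serum phosphate is mixed. In favour, Section 1.4 gives hypophosphatemia at 4.3 versus 0.9 per 100 person-years in HIV-infected children with and without Tenofovir DF. It also reports that all 7 adults with tubular dysfunction in one series had hypophosphatemia. Against, the same section cites a systematic review that found no clear association, and Section 1.2.3.1 reports no confirmed phosphorus below 2 mg/dL over 72 weeks in adolescents with CHB.

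**Working it through.** The plan states no count of phosphorus tests, so there is no figure to reproduce.

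**1. Scheduled draws, Group 1, post-baseline** (Protocol 3.2, 6.4.1 to 6.4.6; SAP Appendix 1)
- Renal chemistry: Weeks 4, 12, 24, 36, 48, 60, 72, 84, 96 = 9.
- Bone chemistry, with phosphorus: Weeks 24, 48, 72, 96 = 4.
- Renal draws without listed phosphorus: 9 − 4 = 5 (Weeks 4, 12, 36, 60, 84).

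**2. Delay to the next scheduled value.** Assume onset is uniform over 96 weeks. Mean wait = Σ(interval²) / (2 × 96).
- Now, four 24-week intervals: 4 × 24² / 192 = 2304 / 192 = 12.0 weeks.
- With the change, intervals of 4, 8 and seven of 12 weeks: (16 + 64 + 7 × 144) / 192 = 1088 / 192 = 5.7 weeks.
- Difference: 6.3 weeks. The longest gap falls from 24 to 12 weeks.

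**3. Number of cases concerned.** The rates are those in Protocol 1.4. They come from HIV-infected children and their case definition is not given, so the results are a range and not a forecast.
- Planned Group 1: 50 × 96 × 7 / 365.25 = 92.0 person-years. Cases: 92.0 × 0.043 = 4.0, or 92.0 × 0.009 = 0.8. A quarter (24/96) would start before Week 24: 1.0 or 0.2.
- Enrolled Group 1: at most 15 × 96 × 7 / 365.25 = 27.6 person-years. Cases: at most 1.2 or 0.2.

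**4. How far the negative adolescent result reaches.** With 0 of 52 treated subjects below 2 mg/dL, the one-sided 95% upper limit is 1 − 0.05^(1/52) = 5.6%. The 2 mg/dL threshold is also stricter than 3.0 mg/dL.

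**5. Imbalance between groups.** Group 2 has scheduled post-baseline phosphorus at Weeks 48 and 96 only. Suppose each test has the same independent chance p of a flag; the any-time chance over k tests is 1 − (1 − p)^k. The documents do not give p, so 1% and 5% are assumptions.

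| p | k = 2 (Group 2) | k = 4 (Group 1 now) | k = 9 (Group 1 changed) | Ratio now | Ratio changed |
|---|---|---|---|---|---|
| 1% | 2.0% | 3.9% | 8.6% | 2.0 | 4.3 |
| 5% | 9.8% | 18.5% | 37.0% | 1.9 | 3.8 |

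At k = 9, 1% flags about 0.086 × 50 = 4.3 of the planned Group 1 subjects, close to the 4.0 cases in step 3. At 5% it flags about 0.37 × 50 = 18.5. The upper value is therefore well above what the cited rate suggests, unless the 3.0 mg/dL cut-off catches many values that the cited study did not count.

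**The case against.** The strongest case on the other side is that this is a preference about frequency. Section 7.5.5 sets no interval, unscheduled phosphate tests are not forbidden, and the renal schedule is said to follow the SmPC. A reader might infer that the schedule contradicts 7.5.5, or that phosphate was never tested between bone visits. The documents support neither. They show only that serum phosphorus is not listed at those draws.

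Second, the gain is smaller than step 2 suggests. Urine phosphate, urine glucose, urine protein and serum creatinine are collected at all nine Group 1 visits, as are the blood glucose, blood potassium and urine glucose that 7.5.5 asks for. Only a case that first shows as low serum phosphate is found sooner. This stands, so 6.3 weeks and the case numbers are upper bounds. It does not close the gap, because urine phosphate does not trigger 7.5.5.

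Third, the change widens unequal ascertainment. Protocol 8.6.3 and SAP 7.2.2.1 count an abnormality at any time post-baseline, so the summary would rest on 9 versus 2 scheduled tests. This is a real cost. A summary limited to the shared Weeks 48 and 96 equalises the scheduled counts, and a reader might infer that it removes the problem. It does not. A Group 1 case found early may be corrected, or the drug interrupted, before Week 48. Group 2 may also have local-care tests whose number is unknown. Because SAP 7.2 plans no inferential statistics for laboratory data, the harm is to a descriptive comparison.

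Finally, Protocol 8.2.1.1 groups phosphorus with bone biomarkers. A reader might infer that the 24-weekly windows of SAP Table 3-2 would discard the added values. The SAP does not support this. Its list of bone biochemical markers in 7.3 omits phosphorus, and Appendix 3 puts phosphorus in Table 21.2 with calcium and creatinine, apart from the markers in Tables 22.1 to 22.6. The Table 3-1 windows therefore already apply, and they keep all nine visits.

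**Conclusion.** The point holds as a cheap improvement of minor to moderate weight. The count of 5 of 9, and the first scheduled on-treatment value at Week 24, follow directly from the visit lists. The fall in mean wait to 5.7 weeks rests on uniform onset and full attendance, and is an upper bound on the benefit. At the planned size, the cases that could start before Week 24 number about 0.2 to 1.0 in Group 1, using rates from a different population. Group 2 gains nothing from the change.

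The trial closed early, with 30 subjects enrolled and two completing 96 weeks (SAP 1.4 and 2.1). The point therefore concerns the protocol as designed and cannot change the data collected.

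**What to change.** **Protocol.** Add serum phosphorus to the Group 1 serum renal chemistry panel at Weeks 4 to 96, in the synopsis, 3.2, 6.4.1 to 6.4.6 and the Appendix 2 definitions. Appendix 2 has one renal definition for both groups, so mark the addition as applying to Group 1 only. At Weeks 24, 48, 72 and 96 one result serves both panels. Leave 7.5.5 and the Group 2 local-care schedule unchanged.

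**SAP.** Alongside the any-time count, report treatment-emergent phosphate abnormalities by group at Weeks 48 and 96 only (2 versus 2 scheduled tests). State that this equalises scheduled testing but does not fully remove the imbalance. The windows need no change.

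**Cost.** Five extra assays per Group 1 subject on fasting blood already drawn, with no extra visit: 5 × 50 = 250 at the planned size, at most 5 × 15 = 75 at the enrolled size. The share of values below 3.0 mg/dL is unknown. At an assumed 1% to 5%, repeat tests number 2.5 to 12.5 (planned) or 0.75 to 3.75 (enrolled), with a work-up for those confirmed.

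More Grade 1 flags are also likely at age 14 or under, where Grade 1 is 3.0 to 3.5 mg/dL. Above 14, Grade 1 runs from 2.0 mg/dL to a lower limit of normal that the documents do not give, so a value below 3.0 mg/dL might be ungraded and still trigger 7.5.5.
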